8 MANAGEMENT OF MEDICAL DEVICE

8.1 Description

The following devices and equipment will be required for each subject. Those indicated by asterisk (*) are to be sourced and provided by the sponsor and those indicated by "IP" are defined as investigational products:

- Medical Measurement Systems (MMS) Nexam Urodynamic System already in use by the site, or on loan from the Sponsor
- Uroflowmetry device configured with the UDS equipment and computer pressure-flow studies, already in use by site (optional)
- One e·Sense® 7Fr Abdominal Catheter per subject (*) (IP)
- One e·Sense® 7Fr Single Sensor Bladder Catheter or one e·Sense® 7Fr Dual Sensor Urethral Catheter per subject (*) (IP)
- EMG cable (optional component at the discretion of the site)
- EMG patches (optional component at the discretion of the site)
- Nexam wireless remote (optional component at the discretion of the site)
- Wireless Patient Unit (WPU)
- Pump tubing (*)
- 1000 mL beaker (optional)
- One saline bag per subject
- Tape
- Lubricant
- Gloves
- Any other supplies deemed necessary for conducting a UDS study

The clinical trial agreement (CTA) will further specify the equipment and disposables that will be provided to the site.

Note: The CTA will supersede materials provided by Laborie listed above.

	e·Sense® Clinical Investigation Protocol	CLN-00021-ESNS-PH01-PR-01	Version B
---	---	---------------------------	-----------

Note: Monitoring of electromyography (EMG) activity is considered optional at the discretion of the site and is not included in analysis of study endpoints. The measurement of UDS pressures is not influenced by EMG activity also being measured simultaneously.

8.2 Regimen

N/A – there is no treatment regimen required as part of this study.

8.3 Assignment to Groups

No stratification of subjects will be utilized based on study design.

8.4 Preparation and Handling

The UDS system and e·Sense® catheters will be prepared and maintained by the physician or delegated site personnel.

8.5 Packaging and Labelling

Investigational device labelling will appear on all investigational materials under Laborie's and national regulations. A copy of the investigational label is shown in the Investigator's Brochure.

8.6 Device Accountability

All e·Sense® devices used directly for UDS procedures on enrolled subjects must be recorded using the device LOT number on the subjects CRF form and inventory control log. Any unused investigational devices shall be returned to the sponsor. The sponsor will provide the appropriate instructions for their safe return.

8.6.1 Laborie to Study Site:

All investigational devices or equipment transferred between Laborie and the study site must be recorded through the Inventory Control Log. This includes postal deliveries and any deliveries made in person by Laborie. Any equipment or devices that are not used and are not returned to Laborie must also be recorded on the Inventory Control Log. It is Laborie's responsibility to ensure that all inventory both at Laborie and the study site correlate. All investigational device accountability will be recorded through the Inventory Control Form.

8.6.2 Study Site Usage:

All investigational devices used directly for testing subject samples must be recorded on the Inventory Control Form. All investigational devices used by the study site that are not directly used for the testing of subject samples must also be recorded on the Inventory Control Form. This includes any devices used for training or demonstration or any devices which are noted to be defective when opened. All non-investigational devices or material usage will not be recorded or traced.

8.6.3 Study Site to Laborie:

Any equipment or devices that are not used and are returned to Laborie must be recorded on the Inventory Control Form.

	e·Sense® Clinical Investigation Protocol	CLN-00021-ESNS-PH01-PR-01	Version B
---	---	---------------------------	-----------

When the devices have been received by Laborie, it is Laborie's responsibility to ensure that all inventory control forms, both at Laborie and at the study site, correlate.

Note: All investigational devices must be returned to Laborie, however, non-investigational materials/accessories can be left at the site for continued use or returned as agreed upon with the sponsor. Please reference the CTA for further details.

8.7 Concomitant Treatment

Not applicable for this study.

8.8 Subject Compliance Monitoring

Not applicable for this study.

9 ASSESSMENT OF INVESTIGATIONAL DEVICE

9.1 Endpoints

The ESNS-PH01 study consists of one primary objective, one secondary objective and four exploratory objectives.

Primary Objective:

The primary endpoint will be measured by recording the clinician safety and effectiveness rating for each subject on their CRF. The clinicians will indicate whether each of the e·Sense® bladder and abdominal catheters are safe & effective for urodynamic use in at least 30 enrolled subjects. Given the intended use of the device, and the fact that there is no single or combined objective measures generated from the UDS test that can establish the safety and effectiveness, it is justified to obtain clinicians' feedback via a binary response whether the device is safe and effective for urodynamic use.

Secondary Objective:

The secondary endpoint will be measured by recording the number of severe complications and serious adverse events for each subject on their CRF. Due to the low risk profile of UDS, the sponsor would like to report the severe complication-free rate for any severe complications associated with UDS, and therefore this secondary safety endpoint was planned. Additionally, the sponsor would like to collect and assess this information due to a lack of available published data using the e·Sense® catheter technology.

First Exploratory Objective:

The first exploratory endpoint will be measured by collecting usability data in a questionnaire format. At the end of each clinic day a trained clinical user shall complete the questionnaire on CRF 3. When evaluating the usability of a device, the sponsor feels it's appropriate to use a subjective ordinal scale response while assessing human and device usability factors.

	e·Sense® Clinical Investigation Protocol	CLN-00021-ESNS-PH01-PR-01	Version B
---	---	---------------------------	-----------

Second Exploratory Objective:

The second exploratory endpoint will be measured by collecting subject feedback regarding the level of discomfort and pain experienced during their Urodynamic test using the Numerical Pain Rating Scale (NPRS) on CRF 4. Subjects will grade their discomfort/pain on the NPRS from 0 (“No Pain”) to 10 (“Worst Pain”). Given the subject population, use of the NPRS is a validated tool in evaluating pain ratings in adults¹⁰⁻¹².

Third Exploratory Objective:

The third exploratory endpoint will be measured by recording initial resting pressures using the updated e·Sense® catheters while each subject is positioned in a sitting, standing and supine position, if patient mobility allows. Resting pressures will be recorded on each subjects' CRF 1 during their UDS visit. Resting pressure is considered an important quality control parameter in urodynamics^{9,13,14,16}. As described in the Good Urodynamic Practices⁹ (albeit in the context of WFC), the initial intravesical and abdominal resting pressures are real, are different between patients, and depend significantly on patient's position. The sponsor would like to collect and assess initial resting pressures for the e·Sense® catheters, due to a lack of available published data using the e·Sense® catheter technology.

Fourth Exploratory Objective:

The fourth exploratory endpoint will be measured by recording resting pressures using the updated e·Sense® catheters during various points of the UDS test as applicable (every 100 mL of filling, MCC, and post-void) at the recorded patient position (sitting, standing, or supine). Patients are to remain in the same position throughout, however supplemental positions can be used (e.g. performing provocative manoeuvres). Resting pressures and patient position will be recorded on each subjects' CRF 1 during their urodynamics visit. Again, resting pressure is considered an important quality control parameters in urodynamics^{9,13,14,16}. The sponsor would like to collect and assess resting pressures during the UDS test for the e·Sense® catheters, due to a lack of available published data using the e·Sense® catheter technology.

Table 4 shows the relationship between all study endpoints and case report forms.

Table 4. CRF data and relationship to study objectives

Case Report Form	Relationship of data recorded to study objectives
CRF 1 (UDS Visit)	Primary endpoint for safety and effectiveness Third and fourth exploratory endpoints for UDS
CRF 2 (Relevant Medical History)	N/A – Collected for patient demographic and eligibility reasons
CRF 3 (Clinical User Questionnaire)	First exploratory endpoint for usability evaluation
CRF 4 (Subject Questionnaire)	Second exploratory endpoint for discomfort/pain levels
CRF 5 (Adverse Events)	Secondary safety endpoint for adverse events and severe complications. Supports primary endpoint and collected for safety data collection purposes

	e·Sense® Clinical Investigation Protocol	CLN-00021-ESNS-PH01-PR-01	Version B
---	---	---------------------------	-----------

Case Report Form	Relationship of data recorded to study objectives
CRF 6 (Device Deficiency)	Supports primary endpoint and collected for safety data collection purposes
CRF 7 (Follow-Up)	Supports secondary safety endpoint for adverse events and severe complications. Supports primary endpoint and collected for safety data collection purposes.

9.2 Methods of Assessment

The e·Sense® catheters will be used to assess and record bladder pressure (vesical and/or urethral - for applicable subjects) and abdominal pressure, which are in turn interpreted by the clinician to identify UDS events. These measurements will be recorded using an MMS Nexam UDS system. The resulting interpretations and conclusions regarding safety, effectiveness, and usability of the investigational device, will be made by the Investigator overseeing the subject's case on the relevant case report form.

All study outcome data captured will be compiled and analysed by the Laborie study team to determine if the endpoints were successfully achieved based on whether the null hypotheses were rejected.

10 PATIENT SAFETY

10.1 Definitions

Investigators shall refer to the Safety Reporting Guidelines (ESNS-PH01-SRG-01) for country-specific safety definitions and requirements, which includes the provisions of Article 80 of MDR (EU) 2017/45 prevailing over the public health code in EU Member States, where applicable.

10.1.1 Adverse Events (MDR EU 2017/45):

Any untoward medical occurrence, unintended disease or injury, or untoward clinical signs, including abnormal laboratory finding, in subjects, users or other persons, in the context of a clinical investigation, whether or not related to the investigational medical device

NOTE 1 This definition includes events related to the investigational medical device or the comparator.

NOTE 2 This definition includes events related to the procedures involved.

NOTE 3 For users or other persons, this definition is restricted to events related to investigational medical devices.

	e·Sense® Clinical Investigation Protocol	CLN-00021-ESNS-PH01-PR-01	Version B
---	---	---------------------------	-----------

10.1.2 Adverse Device Effect (ISO14155:2020):

Any adverse event related to the use of an investigational medical device.

NOTE 1 This definition includes adverse events resulting from insufficient or inadequate instructions for use, deployment, implantation, installation, or operation, or any malfunction of the investigational medical device.

NOTE 2 This definition includes any event resulting from use error or from intentional misuse of the investigational medical device.

NOTE 3 This includes 'comparator' if the comparator is a medical device.

10.1.3 Device Deficiency (MDR EU 2017/45):

Any inadequacy in the identity, quality, durability, reliability, safety or performance of an investigational device, including malfunction, use errors or inadequacy in information supplied by the manufacturer.

10.1.4 Serious Adverse Event (MDR EU 2017/45):

Any adverse event that led to any of the following:

- a) death;
- b) serious deterioration in health of the subject, that resulted in any of the following:
 - i. life-threatening illness or injury,
 - ii. permanent impairment of a body structure or a body function,
 - iii. hospitalisation or prolonged hospitalization,
 - iv. medical or surgical intervention to prevent life-threatening illness or injury or permanent impairment to body structure or a body function,
 - v. chronic disease,
- c) foetal distress, foetal death or a congenital physical or mental impairment or birth defect.

NOTE per ISO 14155: Planned hospitalization for a pre-existing condition, or a procedure required by this protocol, without serious deterioration in health, is not considered a serious adverse event.

10.1.5 Unanticipated Serious Adverse Device Effect (ISO14155:2020):

Serious adverse device effect which by nature, incidence, severity or outcome has not been identified in the current risk assessment.

NOTE: Anticipated serious adverse device effect (ASADE) is an effect which by its nature, incidence, severity or outcome has been identified in the risk assessment.

10.1.6 Severe Complications (sponsor definition):

A severe complication is defined an adverse event (whether expected or non-expected) that has been evaluated on CRF 5 as:

- Severity graded as either Severe (3) or Life-Threatening (4) and;

	e·Sense® Clinical Investigation Protocol	CLN-00021-ESNS-PH01-PR-01	Version B
---	---	---------------------------	-----------

- Study Procedure Relationship graded as Probably Related (3) or Definitely Related (4) and;
- Action taken with respect to study device required Invasive Medical Intervention (4) and/or resulted in Hospitalization (5) and;
- The outcome for the subject resulted in recovered with Major Sequelae (3), Ongoing/Continuing Treatment (4), Condition Worsened (5) or Death (6).

Or otherwise any adverse event categorized as a Serious Adverse Event (See Section 10.1.4 for definition).

NOTE: An invasive medical intervention refers to any medical intervention or oral medication treatment lasting one week (seven days) or longer. Conversely, a non-invasive treatment refers to any medical intervention or oral medication lasting less than one week (seven days).

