7.5 Follow-Up

Study staff will telephone each subject three to five days post-test to inquire about possible adverse events that may have occurred after their UDS test. All follow-up call details will be recorded on the follow-up CRF (ESNS-PH01-CFR-07) and update the subjects' adverse event form (ESNS-PH01-CRF-05), where applicable.

The focus of the follow-up call is to gather information about study-related adverse events, which are adverse events that are possibly, probably or definitely related to the study procedure.

For subjects who did not experience any adverse events or were not experiencing symptoms at the time of their follow-up call, their direct involvement in the study ends at the time of the telephone follow-up call. All subjects who did experience adverse events will be followed until resolution, and this information shall be recorded on the subject's CRF (ESNS-PH01-CRF-01) and adverse event form (ESNS-PH01-CRF-05).

	e·Sense® Clinical Investigation Protocol	CLN-00021-ESNS-PH01-PR-01	Version B
---	---	---------------------------	-----------

In the case of persistent adverse events, regular follow-up will be performed by study staff until resolution, at which point the subject's direct involvement in the study will end. Any follow-up medical intervention prescribed and frequency of future follow-ups to treat an adverse event, will be at the discretion of the Investigator.

Since subjects who experience adverse events are being followed until resolution, the length of time a subject is participating in the study can vary. A subjects participation will end if they report no adverse events at the three to five day follow-up call, or when the reported adverse event has resolved.

Follow-up on any treatment decisions made by the Investigator are not the focus of the present study and will not be followed up. Only adverse events related to the urodynamics procedure or use of the investigational device are the focus of the present study.

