11.7 Interim Analysis

Once 30 primary analysis population subjects complete the study the primary composite safety and effectiveness analysis will be conducted for regulatory purposes. Once all (60-65) subjects are complete, the secondary endpoint analysis will be performed. In addition, the exploratory endpoints will be assessed and an exploratory analysis of the composite (primary) safety and effectiveness endpoint including all subjects will be performed.

There are currently no criteria for stopping the study early on statistical grounds. Refer to Section 5.3 for details about suspension or premature termination.

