12.4 Case Report Form (CRF) & Source Documents

All study staff will be trained on the protocol requirements, CRF and questionnaire completion, and their training documented. It is the responsibility of the Investigator to maintain adequate

	e·Sense® Clinical Investigation Protocol	CLN-00021-ESNS-PH01-PR-01	Version B
---	---	---------------------------	-----------

and accurate CRFs designed by Laborie to record all observations and other data pertinent to the clinical investigation. All CRFs and questionnaires should be completed in their entirety in a neat, legible manner to ensure accurate interpretation of data. Should a correction be made, the information to be modified must not be overwritten, but rather crossed out, corrected and initialled by the study staff member authorized to make entries and/or corrections to the CRFs. Source documents worksheets for recording data will be created as agreed upon by the sponsor or the site, as required. Data from the source documents should be entered into the CRF after each subject's visit.

To confirm the quality of the study, pseudonymized UDS data files will be requested by the sponsor for each subject. A unique subject code will be assigned to each subject based on the site number and sequential subject number (e.g. 101-001). The Investigator is responsible for maintaining subject identifying information strictly confidential, secure and inaccessible to unauthorized persons. CRFs will be treated as source data in the event that the original information is entered on the CRFs first (and no source document worksheet is utilized for that data point).

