13 MONITORING, AUDITING, AND INSPECTING

13.1 Study Monitoring Plan

Laborie is responsible for developing a monitoring plan prior to study initiation, the monitoring plan will consist of a risk-based approach depending on monitoring needs for the clinical investigation.

The Investigator agrees to provide reliable data and all information requested by the Clinical Investigation Protocol (with the help of the CRFs, questionnaires or other appropriate

	e·Sense® Clinical Investigation Protocol	CLN-00021-ESNS-PH01-PR-01	Version B
---	---	---------------------------	-----------

instrument) in an attributable, legible, complete, original, and accurate according to the instructions provided and to ensure direct access to source documents to Sponsor representatives. Any changes to the sourced data shall be traceable and not obscure the original entry.

The Sponsor of this Clinical Investigation is responsible to Health Authorities for taking all reasonable steps to ensure the proper conduct of the Clinical Investigation Protocol as regards ethics, Clinical Investigation Protocol compliance, integrity and validity of the data recorded on the CRFs and questionnaires. Thus, the main duty of the Monitoring Team is to help the Investigator and the Sponsor maintain a high level of ethical, scientific, technical and regulatory quality in all aspects of the Clinical Investigation.

At regular intervals during the Clinical Investigation, the site will be contacted, through monitoring visits, letters or telephone calls, by a representative of the Monitoring Team to review study progress, Investigator and subject compliance with Clinical Investigation Protocol requirements, and any emergent problems. The monitoring plan will describe the frequency, extent, and nature of monitoring.

During these monitoring visits, the following but not exhaustive list of points will be inspected with the Investigator: subject informed consent, subject recruitment and follow-up, Serious Adverse Event documentation and reporting, outcome events documentation and reporting, Investigational Product allocation, Investigational Product accountability, use and quality of data.

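### Does the missing time point for the outcome code in section 10.1.6 leave the severe complication-free rate undefined?

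*Combined protocol and SAP*

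**What the plan says.** Section 10.1.6 gives two routes to a severe complication. The first needs four CRF 5 gradings together: severity (severe or life-threatening), relationship to the procedure (probable or definite), action taken (invasive intervention and/or hospitalization), and outcome. The outcome criterion is "The outcome for the subject resulted in recovered with Major Sequelae (3), Ongoing/Continuing Treatment (4), Condition Worsened (5) or Death (6". The second route has no outcome condition: "Or otherwise any adverse event categorized as a Serious Adverse Event (See Section 10.1.4 for definition". A note to the section sets the meaning of the action criterion: "An invasive medical intervention refers to any medical intervention or oral medication treatment lasting one week (seven days) or longer".

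On follow-up, section 7.5 states "All subjects who did experience adverse events will be followed until resolution". After the call at three to five days, staff are to "update the subjects' adverse event form (ESNS-PH01-CRF-05), where applicable". A subject's participation ends at that call if there is nothing to report, and otherwise when the event has resolved. Section 7.4 places the end of the study after all follow-up and data collection. Section 11.7 then says "Once all (60-65) subjects are complete, the secondary endpoint analysis will be performed".

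Neither section 10.1.6 nor section 11.2.1 names the date at which the outcome code is read.

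**The concern.** The outcome list mixes end states, such as major sequelae and death, with a passing one, continuing treatment. A passing state needs a time point. Take an event that is graded severe, is related to the procedure, is treated for a week or more and is not serious. Coded during treatment it carries code 4. Coded after recovery without major sequelae it presumably carries one of the codes not listed in section 10.1.6. The same clinical course could then count or not count, depending on when the form was filled in.

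That matters because the secondary test has no room for a single event, the study is open-label, and the sponsor both classifies the events (section 10.3) and analyses them (section 9.2). If the code at database lock were used, the enrolment date might also matter. Table 2 plans the first 30 subjects for June to December 2020, the rest for September to December 2021, and the lock for January 2022.

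**Working it through.** **1. The test.** Inputs from sections 11.2.1 and 11.2.2: target 95%, one-sided level 5%, n from 60 to 65, assumed true rate 100%. With no events the Clopper-Pearson lower limit is 0.05^(1/n) and p = 0.95^n. With one event p = 0.95^n + n × 0.05 × 0.95^(n−1).

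| n | events | lower limit | p | null rejected |
|---|---|---|---|---|
| 60 | 0 | 0.05^(1/60) = 0.9513 | 0.0461 | yes |
| 60 | 1 | 0.9234 | 0.0461 + 3 × 0.0485 = 0.192 | no |
| 65 | 0 | 0.05^(1/65) = 0.9550 | 0.0356 | yes |
| 65 | 1 | 0.9291 | 0.0356 + 3.25 × 0.0375 = 0.158 | no |

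The rule is zero events throughout. One event is tolerated only from n = 93 (lower limit 0.95001; n = 92 gives 0.9495). Power at a true rate of 100% is exactly 100%, against the stated 99%, so the plan's figure is reproduced to within one point. The exact type I error at n = 60 is 4.6%.

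**2. Which code the text points to.**
- Section 10.1.6 speaks of what the outcome for the subject resulted in, which is the language of an end result.
- Section 7.5 follows each event to resolution and keeps CRF 5 current.
- Section 7.4 ends the study only after all follow-up.
- Section 11.7 runs the secondary analysis after that.

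The code available at analysis is therefore the last one recorded at the end of follow-up. Code 4 still has a use there, for an event that persists and is under treatment when the data are locked.

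**3. Whether an event counts at the telephone call.** The four criteria are joined by *and*. For a non-serious event the action criterion in practice means treatment lasting seven days or longer. A course begun on or after the test day has run at most 5 days at the call, and 5 < 7. Unless planned duration is taken as enough, the event does not yet qualify. The definition itself looks past the call, to a later contact of the kind section 7.5 provides.

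**4. How often it could matter.** The documents give no rate for such events. The nearest figure is urinary tract infection in about 2–4% (section 3.6), which is not a rate of severe events. Assume that 5% to 25% of these meet the severity, relationship and duration criteria and are not serious. The event rate r then runs from 0.02 × 0.05 = 0.1% to 0.04 × 0.25 = 1.0%. The chance of at least one event in 60 is 1 − (1 − r)^60, or 5.8% to 45.3%. These are upper bounds on the chance that coding time decides the test. Timing is irrelevant if the event ends in code 3, 5 or 6, if treatment is still running at lock, or if a serious event has already failed the test.

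**5. What worst-ever scoring would do.** Every event that qualifies through a long course of treatment is under treatment at some time. If a code were taken at the call and the worst code kept, nearly all such events would carry code 4 and the outcome criterion would exclude almost nothing. At assumed rates of 0.1%, 0.5% and 1%, the chance of passing at n = 60 would be 0.999^60 = 94%, 0.995^60 = 74% and 0.99^60 = 55%. Subjects already seen have only the codes that happened to be entered, while later subjects would have an added early code, so the two groups would be scored differently.

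**The case for a change.** The strongest reply is that the final-code reading is inferred. Section 7.5 does not say that the last code defines the endpoint, and if follow-up always runs to resolution, code 4 would almost never be used, yet the sponsor listed it. A rule that can decide the only secondary hypothesis test should be explicit, and one sentence would do it.

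Part of this stands. The protocol names no date, and the test does turn on one event. But the text is incomplete rather than contradictory, and its sections favour one reading. A code for unresolved events is ordinary on an adverse event form and has a role at lock. CRF 5 and the data management plan (section 12.3) are not among the documents and may state the rule.

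The worry about selective coding is also limited. Section 12.4 requires that "the information to be modified must not be overwritten, but rather crossed out, corrected and initialled", and section 13.1 that "Any changes to the sourced data shall be traceable and not obscure the original entry". A change from code 4 to recovery would be visible. All adverse events are summarised in the study report (section 10.3), so an event that does not count is still reported.

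The enrolment-date argument shrinks to events unresolved at lock. The Table 2 dates are only anticipated, and such events count against the device.

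**Conclusion.** No change to the plan is needed. The time point is unwritten, but an analyst would fill it sensibly with the last CRF 5 outcome at the end of adverse event follow-up, with code 4 applying to events still unresolved at lock. On that reading the endpoint is well defined, the exact type I error is 4.6% at n = 60 and 3.6% at n = 65, and the stated power holds under the assumed 100% rate.

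The exposure is confined to severe, procedure-related, non-serious events treated for a week or more. One such event moves the lower limit at n = 60 from 0.9513 to 0.9234, but the documents do not support a figure for how often this would happen. Worst-ever scoring would put a different endpoint in place of the sponsor's, part-way through an open-label study, and reasonable statisticians would dispute it.

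The conclusion rests on two assumptions: that a cured event receives one of the outcome codes not shown in section 10.1.6, and that the unseen CRF 5 instructions do not direct a different reading.
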